NON-INTERVENTIONAL (NI) STUDY PROTOCOL

Study Information

Title	Effectiveness and Safety of Oral Anticoagulants Among Obese Patients with Non-Valvular Atrial Fibrillation in the Veterans Affairs Population with Medicare
Protocol number	B0661162
Protocol version identifier	1.0
Date	September 14, 2020
Active substance	N/A
Medicinal product	Apixaban
Research question and objectives	
The primary analysis will compare apixaban vs warfarin only.
 
Primary Objectives:
 
Aim 1: Evaluate the demographics and clinical characteristics of obese and severely obese NVAf patients initiating OACs (all patients, standard dose, and low dose).
 
Aim 2: Determine if there is a difference in OAC treatment effect between obese and non-obese and severely obese and non-severely obese patients for stroke/systolic embolism (SE), MB, and net clinical benefit.
 
Aim 3: Compare the risk of stroke/SE, major bleeding, net clinical benefit among obese and severely obese NVAf patients initiating OACs.

Author	PPD [REDACTED] PPD [REDACTED] PPD [REDACTED] PPD [REDACTED] PPD [REDACTED] PPD [REDACTED]
---------------	--

This document contains confidential information belonging to Pfizer. Except as otherwise agreed to in writing, by accepting or reviewing this document, you agree to hold this information in confidence and not copy or disclose it to others (except where required by applicable law) or use it for unauthorized purposes. In the event of any actual or suspected breach of this obligation, Pfizer must be promptly notified.

2. LIST OF ABBREVIATIONS

Abbreviation	Definition
AE	adverse event
AF	atrial fibrillation
ARIC	Atherosclerosis Risk in Communities
BMI	body mass index
CCI	[REDACTED]
CHADS ₂	Acronym: congestive heart failure, hypertension, age 75 years or older, diabetes mellitus
CMS	Center of Medicare Services
CPI	Consumer Price Index
CPT	Current Procedural Terminology
CrCl	creatinine clearance rate
DME	durable medical equipment
DOAC	direct oral anticoagulant
DSS	Decision Support System
EDB	enrollment database
ER	emergency room
GHP	group health plan
GLM	generalized linear models
GPP	Good Pharmacoepidemiology Practices
HAS-BLED	Hypertension, Abnormal Renal/Liver Function, Stroke, Bleeding, Labile INR, Elderly (Age >65 years), Drugs or Alcohol
HCFA	Health Care Financing Agency
HCPCS	Healthcare Common Procedure Coding System
HCRU	Healthcare resource utilization
HHA	Home Health Agency
HR	hazard ratios
ICD-9-CM	International Classification of Disease, Ninth Revision, Clinical Modification
ICD-10-CM	International Classification of Disease, Tenth Revision, Clinical Modification
ICH	intracranial hemorrhage
IPTW	inverse probability treatment weightings
INR	international normalized ratio
LAB	laboratory
LAR	labatory results
LOS	length of stay
MB	major bleeding
NDE	non-destructive examinations
NVAF	non-valvular atrial fibrillation
OAC	oral anticoagulant

Abbreviation	Definition
PHA	pharmacy
PPPM	per patient per month
RAD	radiology
RIF	research identifiable file
RWD	real world data
SE	systemic embolism
SNF	skilled nursing facility
SSN	social security number
TTR	time in therapeutic range
USD	United States dollar
VA	Veterans' Affairs
VHA	Veterans' Health Affairs
VKA	Vitamin K antagonist

4. ABSTRACT

Title: Effectiveness and Safety of Oral Anticoagulants Among Obese Patients with Non Valvular Atrial Fibrillation in the Veterans Affairs Population with Medicare

Rationale and Background: Prior RWD studies have evaluated the use of oral anticoagulants (OAC) in obese patients with atrial fibrillation (AF), but they are limited by sample size or by using ICD-9 diagnosis codes to define obesity. Conducting analyses of different datasets and addressing some of these limitations could add important information about the use of OACs in this population.

Research Question and Objectives: The overall objective of this analysis is to understand patient characteristics, use of treatment, and clinical outcomes among obese and severely obese patients with non-valvular atrial fibrillation (NVAf) who initiate therapy with OACs. The aim of this study is to compare all DOACs to warfarin; however, the primary analysis will be conducted among apixaban vs warfarin patients only. If sample size permits, we will also conduct other DOAC vs warfarin and DOAC vs DOAC analysis.

Study Design: This retrospective observational study will be conducted using linked national patient-level data from the Veterans Affairs (VA) Population and Center for Medicare and Medicare Services (CMS) fee-for-service database. The study period will be from January 1, 2013 through December 31, 2017. The study allows for a 6-month baseline period prior to the index date in the identification period. The index date will be defined as the date of first prescription for an OAC from July 1, 2013 – December 31, 2017; the first direct oral anticoagulant (DOAC) pharmacy claim date during the identification period will be designated as the index date. The first warfarin prescription date will be designated as the index date for patients without any DOAC claim. Patients will be required to have ≥ 1 AF medical claim in any position in the inpatient or outpatient setting before or on the index therapy date. Patients will be followed from the day after the index date until the earliest of 30 days after the date of discontinuation, switch, death, end of study period, or end of continuous medical enrollment (Parts A and B).

Population: Obese or severely obese AF patients in the CMS Medicare and Veterans' Health Affairs (VHA) databases who were newly prescribed OACs between January 1, 2013 and December 31, 2017.

Variables: Demographic and clinical characteristics and clinical outcomes including stroke/systolic embolism (SE), major bleeding (MB), and net clinical benefit.

Data Sources: The study will be conducted using linked CMS Medicare fee-for-service databases and Veterans Health Affairs Database.

Study Size: All eligible patients available for analysis will be included.

Data Analysis: Means, medians, and standard deviations will be provided for continuous variables. Numbers and percentages will be provided for dichotomous and polychotomous variables. Bivariate comparisons of baseline characteristics and outcomes measures will be provided. The primary analysis will be conducted among apixaban vs warfarin patients only. Inverse probability treatment weighting (IPTW) will be used to balance patient characteristics when comparing outcomes among different cohorts (for primary and secondary analyses). Appropriate tests (eg, t-test, chi-square test) will be used based on the distribution of the measure. Kaplan-Meier survival curves will be generated to illustrate the time to first Stroke/SE, MB Event, and Net Clinical Benefit. The cumulative incidence rate for clinical outcomes will be calculated. Cox proportional hazard ratio models will be used to evaluate the risk of clinical outcomes. Time to therapeutic range (TTR) will be calculated using the Rosendaal method and will be computed using INR values among warfarin patients during the follow-up. TTR will be calculated based on the percentage of time a patient remained in therapeutic range evaluated during the entire follow-up period. Data analysis will be executed using statistical software SAS version 9.4 (Cary, NC).

5. AMENDMENTS AND UPDATES

None.

6. MILESTONES

Milestone	Planned Date
Completion of protocol development	Draft 1: 1 July 2020
Protocol revisions	Final: 14 August 2020
Start of data collection	10 June 2020
End of data collection	December 2020
Completion of Descriptive Tables	October 2020
Completion of Multivariate Analysis	November 2020
Completion of Dose Subgroup Analysis	December 2020
Final Study Report	December 2020

7. RATIONALE AND BACKGROUND

Atrial fibrillation (AF) is recognized as the most common sustained cardiac arrhythmia in the United States and is associated with a near five-fold excess of stroke.¹ The prevalence of AF was estimated at 5.1 million in 2010 and projected to be 9.3 million in 2030 in the United States with an annual increase of 3.6%.² AF also bears substantial economic burden. The direct health care costs associated with AF were estimated at approximately \$6 billion annually.³

Vitamin K antagonists (VKAs; ie, warfarin) have been the mainstay treatment for stroke prevention among AF patients, reducing stroke by approximately 60%.⁴ Over the past 25 years, VKA use has been expanded from preventing stroke in valvular disease-associated AF patients to patients with non-valvular AF (NVAF).⁴

Warfarin therapy requires close monitoring of the international normalized ratio (INR). The INR range from 2.0 to 3.0 (therapeutic range) was proven to be efficient in stroke prevention among AF patients, and is recommended in the treatment of AF.^{5,6} However, due to its limited therapeutic index and possible drug and food interactions, only about half of AF patients in the United States receive warfarin therapy as recommended.⁷

Over the last several years, direct oral anticoagulants (DOACs), including apixaban, dabigatran, edoxaban, and rivaroxaban, were approved in the United States for stroke prevention among NVAF patients. Clinical trials demonstrated that DOAC use has shown stroke risk reduction similar or superior to warfarin, and lower or similar rates of bleeding.⁸⁻¹¹ In the years since their approval, DOACs have been increasingly preferred over warfarin due to

the convenience of fewer routine monitoring visits, no requirements for dose adjustment, and limited dietary interactions.

Obesity, another prevalent health condition in the United States, had an age-adjusted prevalence of 39.8% in 2015-2016.¹² In the Atherosclerosis Risk in Communities (ARIC) study, obese and overweight individuals accounted for 17.9% of all AF cases;¹³ Additionally, obese patients have a 49% increased risk of AF compared with non-obese patients.¹⁴ Obese patients have been included in RCTs of DOACs and these studies did not show different results by weight.¹⁵⁻²⁰ However, the severely obese population (BMI 40) has a more limited representation in RCTs.^{19,20} With the current fixed-dose DOAC prescriptions, the clinical impact of anticoagulation on NVAf patients with obesity is expected to be similar, provided patients have optimum peak and trough levels of DOACs.²¹

Real world data (RWD) examining the use of oral anticoagulants (OACs) in obese and severely obese patients is limited by sample size or by using ICD-9 diagnosis codes to define obesity, with most literature focusing on outcomes of AF regardless of intervention.²² ARISTOPHANES obesity subgroup analysis found that in obese patients, apixaban was associated with lower risk of stroke/systemic embolism (SE) and major bleeding (MB) compared to warfarin. Rivaroxaban was associated with lower risk of stroke/SE but similar risk of MB, whereas dabigatran was associated with lower risk of MB, but similar risk of stroke/SE compared to warfarin.²³ The goal of this study is to evaluate the risk of stroke/SE, MB, and net clinical benefit among obese and severely obese OAC treated patients using VA linked Medicare databases. The results of this linked, retrospective claims analysis will provide unique insight into outcomes of OAC use in obese and severely obese patients as the VA database includes vital measures (BMI, body weight, height) and laboratory results (INR, TTR) in addition to typical health outcomes from Medicare claims data.

8. RESEARCH QUESTION AND OBJECTIVES

8.1. Study Objectives

The overall objective of this analysis is to understand patient characteristics, treatment effect, and clinical outcomes among obese and severely obese patients with NVAf who initiate therapy with OACs (all patients, standard dose, and low dose). The primary analysis will be conducted among apixaban vs warfarin patients only.

8.1.1. Primary Objectives

Aim 1: Evaluate the demographics and clinical characteristics of obese and severely obese NVAf patients initiating OACs (all patients, standard dose, and low dose; primary analysis will compare apixaban vs warfarin).

Aim 2: Determine if there is a difference in OAC treatment effect between obese and non-obese and severely obese and non-severely obese patients for stroke/SE, MB, and net clinical benefit.

Aim 3: Compare the risk of stroke/SE, MB, net clinical benefit among obese and severely obese NVAF patients initiating OACs (primary analysis will compare apixaban vs warfarin).

8.1.2. Secondary Objectives

Aim 4: A secondary analysis will also evaluate the following among warfarin treated obese and severely obese patients:

- Distribution of international normalized ratio (INR; <2, 2-3, >3).
- Distribution of time in therapeutic range (TTR \geq 65% [good] and TTR <65% [poor]).
- Compare the baseline characteristics of patients with good vs poor TTR.

CCI

9. RESEARCH METHODS

9.1. Study Design

9.1.1. Key Index Period Definitions

[figure not shown]
- **Study Period:** The study period will range from January 1, 2013 through December 31, 2017.
- **Patient Identification Period:** The identification period will range from July 1, 2013 until December 31, 2017, allowing for a 6-month baseline period prior to the index date.
- **Baseline Period:** The baseline period will be 6 months prior to, and on, the index date.
- **Follow-up Period:** The follow-up period will be defined as the time period between the day after the index date and end of study period (December 31, 2017). Patients will be followed from the day after the index date to 30 days after the date of discontinuation, switch, death, end of study period, or end of continuous medical enrollment (Parts A & B), whichever is earlier.

9.1.2. Key Index Point Definitions

- **Index Therapy Date:** The index date will be defined as the date of first prescription for an OAC from July 1, 2013 – December 31, 2017; the first DOAC pharmacy claim date during the identification period (July 1, 2013-December 31, 2017) will be designated as the index date. The first warfarin prescription date will be designated as the index date for patients without any DOAC claim.
- **AF Diagnosis:** Evidence of AF diagnosis must be present, as evidenced from 1 or more claims for AF in any position in the inpatient or outpatient setting, before or on the index therapy date.

Study Design Figure (for Illustration Purposes, May Not Be Proportionate):

Figure 1. Study Design

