Atrial fibrillation patients that receive a prescription for an OAC (warfarin, apixaban, dabigatran, edoxaban, or rivaroxaban) other than the index drug prescription during the follow-up period will be considered switchers if this OAC prescription is within ± 30 days of last days' supply. The follow-up will be censored at the switching of the index drug.

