9.2.1. Inclusion Criteria

Patients must meet all of the following inclusion criteria to be eligible for inclusion in the study:

- Obese or severely obese.
- Initiated an OAC from July 1, 2013 - December 31, 2017; the first DOAC pharmacy claim date during the identification period will be designated as the index date. The first warfarin prescription date will be designated as the index date for patients without any DOAC claim.
- Individuals ≥ 18 years old as of the index date.
- Had 6 months continuous health plan enrollment with medical benefits (Parts A & B) for at least 6 months pre-index date (baseline period).

- At least 1 diagnosis of AF prior to or on index date, identified by any medical claim associated with an International Classification of Diseases, Ninth Revision, Clinical Modification (ICD-9-CM) code of 427.31 or International Classification of Diseases, Tenth Revision, Clinical Modification (ICD-10-CM) code of I480-I482, and I4891.
- Had body weight or BMI value reported within ± 6 months of the index date.

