9.2.2. Exclusion Criteria

Patients meeting any of the following criteria will not be included in the study:

- Had medical claims indicating a diagnosis or procedure of rheumatic mitral valvular heart disease, heart valve replacement/transplant, venous thromboembolism, or transient AF 6 months prior to or on the index date.
- Had hip/knee replacement surgery within 6 weeks prior to or on the index date.
- Were pregnant during the study period.
- Had an OAC prescription during the 6 months pre-index date.
- Had follow-up time equal to 0 days.
- Had more than one OAC on the index date.

Flag: A flag will be created to evaluate the mechanical heart valve/mitral stenosis during the 6 months prior to or on the index date using narrow definition.

All codes for the selection criteria are detailed in Appendix [Table 4](#).

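### Warfarin cohort membership depends on never filling a DOAC later, so the primary apixaban versus warfarin hazard ratios are open to selection bias

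*Combined protocol and SAP*

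**What the plan says.** Section 9.1.2 opens with a general rule: "The index date will be defined as the date of first prescription for an OAC from July 1, 2013", running to 31 December 2017. It then gives DOACs precedence. The Abstract words this as "the first direct oral anticoagulant (DOAC) pharmacy claim date during the identification period will be designated as the index date", and Section 9.2.1 repeats it as an inclusion criterion: "the first DOAC pharmacy claim date during the identification period will be designated as the index date". Warfarin is the residual category: "The first warfarin prescription date will be designated as the index date for patients without any DOAC claim". That sentence, which also appears in the Abstract and in Section 9.2.1, does not restrict the DOAC claim to a time before the warfarin start.

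Section 9.1.1 makes the two windows end together: "The identification period will range from July 1, 2013 until December 31, 2017" and "The study period will range from January 1, 2013 through December 31, 2017".

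Two further rules decide what happens to a warfarin starter who later fills a DOAC. Section 9.2.2 excludes anyone who "Had an OAC prescription during the 6 months pre-index date". Section 9.2.3 assigns the remaining patients to a cohort by index drug. For patients who change drug after index, Section 9.2 (Switch) says "The follow-up will be censored at the switching of the index drug".

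**The concern.** Under the DOAC-precedence rule, a patient's place in the reference arm is not known on the day warfarin is started. It is settled by dispensing up to the end of 2017. A warfarin starter who later fills a DOAC is excluded if an OAC was filled in the 6 months before that DOAC, and otherwise moves to that DOAC's cohort from the DOAC date. Either way, the warfarin person-time and any stroke/SE or bleed in it disappear from the warfarin arm. An apixaban starter who changes drug keeps all person-time and events up to the switch. The arms are therefore built by different rules.

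The look-ahead also outlasts follow-up. Follow-up ends 30 days after discontinuation, but a DOAC claim at any later date in the data still removes the patient. A 2013 warfarin starter is exposed to removal for over four years, a late-2017 starter for hardly any time.

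Warfarin is the reference in the primary comparison for stroke/SE, major bleeding and net clinical benefit. The propensity score in Section 9.7.1 conditions on baseline covariates, and the matching in Section 9.7.2 balances pre-index measures. Neither restores people removed because of something that happened after index. The limitations in Section 9.9 do not mention the issue.

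**Working it through.** **Rules side by side**

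| Patient | Under the DOAC-precedence rule |
|---|---|
| Warfarin start, no later DOAC | Warfarin cohort, followed from warfarin start |
| Warfarin start, later DOAC, OAC filled in the prior 6 months | Excluded; warfarin time and events lost |
| Warfarin start, later DOAC, no OAC in the prior 6 months | Indexed on the DOAC; warfarin time and events lost |
| Apixaban start, later a different OAC | Apixaban cohort, censored at switch |

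On this reading no warfarin-indexed patient can ever switch to a DOAC, so the switch rule is empty in that direction.

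**Size of the distortion.** The plan gives no figure to reproduce here. Let p be the share of warfarin person-time removed and e the share of warfarin events removed. The remaining warfarin rate is the true rate times (1 − e)/(1 − p). If the true hazard ratio is 1 and the apixaban rate is unaffected:

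apparent HR = (1 − p)/(1 − e)

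With fatal share f, and a share q of non-fatal events followed by a DOAC claim, e = (1 − f)q. The documents give neither p nor e.

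**Illustration, not an estimate.** From Section 9.5: 4.5 years of entry and 55% warfarin loss. Assumed:
- entry is uniform;
- the 55% is annual, a hazard of −ln(0.45) ≈ 0.80 per year. In the sample-size formula this reading gives 8,101 per cohort against the plan's 7,945, and all eight Table 3 rows within 3%;
- that 0.80 includes switching to a DOAC at s = 0.05, 0.10 or 0.20 per year;
- a DOAC start after stopping warfarin occurs at 0 or 10% per year;
- f = 0.25, with no other deaths.

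First case in closed form (s = 0.05, no later start, λ = 0.80, A = 4.5, e^(−3.6) = 0.0273):
- Share leaving drug before data end: 1 − (1 − 0.0273)/3.6 = 0.7298
- Initiators dropped: (0.05/0.80) × 0.7298 = 4.6%
- Mean on-drug time: 0.7298/0.80 = 0.9123 years
- On-drug time, per initiator, of those who leave before data end: 0.9123 − (1 − 0.0273 × 4.6)/(0.64 × 4.5) = 0.9123 − 0.3036 = 0.6087
- p = 0.0625 × 0.6087/0.9123 = 4.17%

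The rows with a 10% later start come from numerical integration. Simulation of 6 million initiators per scenario agreed with the HRs within 0.01. In the neutral column q = p; the sign flips at q = p/0.75.

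| Switch /yr | Later start /yr | Dropped | p | HR, q = 0 | HR, neutral | HR, q = 50% | Flip at q |
|---|---|---|---|---|---|---|---|
| 5% | 0 | 4.6% | 4.2% | 0.96 | 0.989 | 1.53 | 5.6% |
| 10% | 0 | 9.1% | 8.3% | 0.92 | 0.978 | 1.47 | 11.1% |
| 20% | 0 | 18.2% | 16.7% | 0.83 | 0.952 | 1.33 | 22.2% |
| 5% | 10% | 15.6% | 12.6% | 0.87 | 0.965 | 1.40 | 16.8% |
| 10% | 10% | 19.5% | 16.2% | 0.84 | 0.954 | 1.34 | 21.6% |
| 20% | 10% | 27.1% | 23.4% | 0.77 | 0.929 | 1.22 | 31.2% |

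Checks: (1 − 0.2342)/(1 − 0.75 × 0.2342) = 0.929; (1 − 0.0417)/(1 − 0.75 × 0.50) = 1.533; 1 − 0.2342 = 0.766. With f = 0 the neutral HR is 1.00, so the neutral shift comes wholly from the assumed fatality.

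**Second set of assumptions.** A separate simulation used 1.10 events per 100 person-years, discontinuation of 0.55 per year, event-free switching of 0.05–0.20 per year and post-event switching of 0–0.5 per year. The rule removed about 10–35% of warfarin initiators. The apparent HR ran from 0.71 (0.20 event-free, 0 post-event) to 1.92 (0.05 and 0.5), and was 1.00 when the two rates were equal. Keeping every initiator and censoring at switch returned about 1.10 per 100 person-years.

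**The case against.** The strongest reply is that the text conflicts with itself and does not clearly choose a biased design. The opening of Section 9.1.2 points to the first OAC of either kind. The switch rule lists all OACs and would be idle for warfarin-to-DOAC changes if precedence were literal. A first-OAC design may have been intended, and under it this selection disappears. Figure 1, which is not visible here, might show how the index is assigned. This stands as a reason for caution about intent. It does not remove the need to act, because the specific rule appears in three places, one of them an inclusion criterion, and a programmer following it would build the selected cohort.

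Parts of Section 9.7.2 are redacted, so a further sensitivity analysis cannot be ruled out. It would not correct the primary cohort definition.

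It is also fair that every driver of the illustration is assumed: switching, later starts, fatality and post-event uptake. The q = 50% case is 2 to 12 times the neutral level. The numbers use stroke/SE inputs only, with none for bleeding or net clinical benefit. Re-entry of re-indexed patients into the apixaban cohort is not modelled. The case therefore rests on the mechanism and not on a demonstrated size.

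**Conclusion.** The concern holds for the rule as worded. Reference-arm membership is conditioned on future DOAC dispensing, the two arms are treated differently, and no visible planned analysis corrects it. Direction and size are unknown, because they depend on whether an event makes a later DOAC claim more or less likely, and the documents give no such rates. Under the stated assumptions the rule alone moves a true hazard ratio of 1 to anywhere from 0.77 to 1.53 in the first illustration and 0.71 to 1.92 in the second. It can leave the ratio unchanged when removal is unrelated to events. This must be settled before the cohorts are built: it affects the validity of every primary hazard ratio, and more patients would not cure it.

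**What to change.** In the Abstract and Sections 9.1.2 and 9.2.1, define the index as the first fill of any OAC, warfarin or DOAC, in the identification period with no OAC in the prior 6 months. Assign the cohort from that fill alone and apply switch censoring to both arms. State whether a patient whose first in-period fill fails the washout is excluded or may qualify on a later fill. State also whether censoring falls on the switch date: Sections 9.1.1 and 9.2 can be read as allowing 30 days after it. Censoring at switch can itself be informative, so this change removes the selection but not that separate question.

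In the attrition table, report the warfarin initiators the present rule removes, with their person-time and their stroke/SE and major bleeding events before the DOAC claim. The actual p and e can then go into the formula above.

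The cost is wording in three places and a rerun of cohort selection, all IPTW sets and the matched samples, with no new data. The warfarin cohort grows. The apixaban cohort (about 20,000 in Section 9.5) may shrink, because patients who start apixaban more than 6 months after their last warfarin fill would move to warfarin. If the feasibility analysis used the same rule, which is not stated, its counts and the Table 3 rows based on 1.10 and 0.87 per 100 person-years need rechecking. Timing is tight: the protocol is dated 14 September 2020, with descriptive tables due in October and multivariate analysis in November 2020.
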